2.1.2.4. Annualized FIX consumption

Annualized FIX consumption is similarly defined as that for AIR, except that the consumed dose in the unit of international units per kilogram (IU/kg) and total units will be measured, while AIR only counts frequency of doses. The estimand for the additional secondary objective and associated secondary endpoint, annualized FIX consumption, follows the same approach as described for AIR. A superiority hypothesis test will be performed, comparing data obtained from Pre- and Post-Infusion Period.

2.1.2.5. Other Secondary Endpoints

Other secondary endpoints, such as annualized number of bleeding events (ABR_{total}) of specific type, (spontaneous and traumatic; and untreated bleeding), frequency of target joint bleeds and percentage of the participants without bleeds, will handle intercurrent events in the same way as described for ABR_{total}.

The following parameters will be compared pre PF-06838435 infusion and 12 months post PF-06838435 infusion. The comparisons should reflect general health modification of hemophilia patients.

- Change in joint health as measured by the Hemophilia Joint Health Score (HJHS) instrument.
- Patient Reported Outcomes (PRO) instruments:
 - Haemophilia Quality of Life Questionnaire for Adults (Haem-A-QoL) Physical Health domain;
 - Haemophilia Activities List (HAL) Complex Lower Extremity Activities Component Score;

[figure not shown]
Secondary endpoints include the following parameters assessed throughout the 6-year study period according to the Schedule of Activities (SoA), which evaluate the long-term efficacy of gene therapy treatment for hemophilia. Summaries will be provided for the overall follow-up period, as well as by yearly intervals.

- ABR for total bleeds (treated and untreated);
- ABR for treated bleeds;
- AIR of exogenous FIX;
- Vector-derived FIX:C level by study visit and the geometric mean at each yearly interval.
- Annualized FIX consumption;
- Annualized number of bleeding events of specific type: spontaneous and traumatic, and untreated bleeding;
- Percentage of participants without bleeds (total bleeds and treated bleeds);
- HJHS total score;
- Frequency of target joint bleeds;
- PROs instruments:
 - Haem-A-QoL, Physical Health domain;
 - HAL Complex Lower Extremity Activities Component Score

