### 6.5.1. Allowed Therapy

During the study participants are requested to suspend their FIX prophylaxis regimen after infusion of PF-06838435, but may take:

- FIX replacement therapy is allowed, as needed. The infusion data (specific product, date, time, dosage, reason) is to be recorded in the eDiary.
- For a bleeding event, the investigator / study staff will recommend the appropriate dose of FIX to treat the bleed because the dose of factor concentrate should include the recent steady-state PF-06838435 induced FIX activity levels to avoid overdosing resulting in a potential thrombotic event. The table in [Appendix 8](#) provides guidelines for target FIX levels based on bleed type.
- A participant may resume prophylaxis if the PF-06838435 treatment is not efficacious, defined for this study as:
  - FIX activity after 12 weeks of  $\leq 2\%$  (in the absence of a confirmed FIX inhibitor) as determined by the central laboratory on 2 consecutive samples collected within a 2 week period;and/or
  - Over a 4-week period (in the absence of a confirmed FIX inhibitor);
    - 2 or more spontaneous bleeds into a major joint and/or target joint;or
    - 3 or more spontaneous bleeds (consisting of joint bleeds and/or significant soft tissue/muscle or other site bleeds). Significant spontaneous bleeds are defined as those that lead to a transient or persistent loss of function.

The investigator is to discuss the case with the sponsor's medical monitor prior to resumption of prophylaxis. Dosing of prophylaxis will take into account the current steady-state FIX activity level. A participant who resumes prophylaxis may choose to discontinue it; however, prior to discontinuation, the investigator is to discuss with the sponsor's medical monitor.

Additional allowed therapies include the following:

- COX-2 inhibitors and topical NSAIDs, where medically necessary
- HIV therapy

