The number of bleeding episodes (treated and untreated, excluding procedural bleeds) from Week 12 to Month 15 will contribute to the post-infusion ABR_{total} calculation for each participant, which is the primary endpoint of this study. A noninferiority test of treatment difference in ABR_{total} between pre- and post-infusion with PF-06838435 will be performed, with a NI margin of 3. The endpoint of ABR_{total} will also be calculated for the following designated time periods, such as >Month 15 to Month 24; >Month 24 to Month 36; >Month 36 to Month 48; >Month 48 to Month 60, and >Month 60 to Month 72, and considered as secondary. These secondary endpoints will be referred to as ABR_{total} Year 2, ABR_{total} Year 3, ABR_{total} Year 5, and ABR_{total} Year 6 hereafter in this document.

In addition, ABR_{total} will also be calculated and summarized for the following periods: prior to corticosteroid initiation, during corticosteroid treatment and post-corticosteroid treatment (Section 5.2) for participants in whom corticosteroid are initiated. ABR_{total} during the overall time period (Week 12 to Month 15) for participants who do not have corticosteroid treatment will be presented side by side in the same table.

For participants with incomplete data for the analysis time period, or if a participant has not yet been followed for the full length of the analysis time period, all available data during the analysis period will be annualized and summarized as such. ABR_{total} for each participant will be calculated as below:

 $ABR_{total} = (Number of bleeding episodes (treated and untreated, excluding procedural bleeds) on study during the given$ time period) x 365.25(Date of last day – date of first day +1) in that time period

Bleeding episodes associated with a surgical procedure (perioperative and/or during the surgical rehabilitation period) will not be included in the ABR_{total} calculation.

If prophylaxis FIX regimen is resumed for a participant as defined in Protocol Section 6.5.1, then the time period following the resumption of the prophylaxis regimen will be excluded from the ABR endpoint calculation, which means the bleeding events will be excluded and the time period of observation will be deducted as well. Date and reason of investigator decision to resume FIX prophylaxis will be collected in a CRF. Date of investigator decision will be considered as date of FIX prophylaxis resumption.

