3.2.6. Percentage of Participants Without Bleeds

The percentage of participants without bleeds will be determined for the overall time period, running total (i.e., Week 12 to Month 15, Week 12 to Year 2, Week 12 to Year 3, etc.) and

Week 12 to Month 15, Month 15 to Month 24 (Year 2), and yearly intervals after Month 24. The percentage of participants without bleeding at baseline will be obtained from Pre-Infusion Period, and will also be summarized.

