6.2.6. Percentage of Participants without Bleeding

Percentage of the participants without treated bleeding will be defined in the overall time period after PF-06838435 infusion, the running total time period (i.e., Week 12- Month 15, Week 12-Year 2, Week 12- Year 3, etc.) and with the same time periods as ABR such as Week 12 to Month 15, Year 2 (Month 15 to Month 24), Year 3, Year 4, Year 5 and Year 6.

The percentage of participants without any bleeding (including treated and untreated) will be defined as well in the overall time period after PF-06838435 infusion, the running total time period (i.e., Week 12- Month 15, Week 12-Year 2, Week 12- Year 3, etc.) and with the same time periods as ABR such as Week 12 to Month 15, Year 2 (Month 15 to Month 24), Year 3, Year 4, Year 5 and Year 6.

Descriptive statistics will include the number of participants, frequencies, and the percentage of participants who have/have no bleeding. The Dosed population will be used for this analysis.

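### Applying the ABR resumption rule to the yes/no bleed-free endpoint lets some resumers and participants with partial follow-up count as bleed-free, and the pre- and post-infusion percentages cover windows of different length

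*SAP*

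**What the plan says.** SAP Section 2.1.2.5 places several secondary endpoints under the intercurrent-event handling of the primary endpoint. Among them, the "percentage of the participants without bleeds, will handle intercurrent events in the same way as described for" ABR for total bleeds.

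SAP Section 3.1.1 defines that handling. Once prophylaxis is resumed, the later period is taken out of the calculation, "which means the bleeding events will be excluded and the time period of observation will be deducted as well". For incomplete data, or "if a participant has not yet been followed for the full length of the analysis time period, all available data during the analysis period", what is available is annualised.

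SAP Section 6.2.6 adds: "Percentage of the participants without treated bleeding will be defined in the overall time period after PF-06838435 infusion", and then lists running totals, Week 12 to Month 15, and later yearly intervals. It does the same for any bleeding, uses the Dosed population, and reports counts and percentages. For the comparator, SAP Section 3.2.6 says: "The percentage of participants without bleeding at baseline will be obtained from Pre-Infusion Period". Neither section sets a minimum follow-up, a rule for resumers or a denominator.

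Protocol Section 6.5.1 explains what resumption means: "A participant may resume prophylaxis if the PF-06838435 treatment is not efficacious". One route is FIX activity of 2% or less after 12 weeks, "as determined by the central laboratory on 2 consecutive samples collected within a 2 week period". The other is through bleeding within 4 weeks, for example "2 or more spontaneous bleeds into a major joint and/or target joint". Protocol Section 3 lists the percentage without bleeds among the parameters to be compared before and after infusion.

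**The concern.** A rate has time in its denominator, so removing follow-up removes opportunity to bleed from both parts of the calculation. A bleed-free percentage has no such term. Shortening a participant's counted time only makes it easier for him to be bleed-free.

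The FIX activity route to resumption needs no bleed, and it opens at about the time the counted window opens. A participant who loses expression and resumes a few weeks after Day 82 can therefore contribute a short bleed-free interval and be reported as without bleeds, although the protocol regards his treatment as not efficacious. The same holds for a resumer whose qualifying bleeds all fell before Day 82, if he stays in the denominator. Participants who withdraw early or have not reached Month 15 at the primary analysis are also judged on a partial window.

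The pre/post contrast has a separate weakness: the two percentages come from periods of different length, with no adjustment for exposure. At stake is the interpretation of a secondary endpoint that is easy to quote.

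**Working it through.** The plan gives no expected value for this percentage, so there is no figure to reproduce.

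**Inputs**
- Bleeding rates: 5.0 per year before and 1.5 per year after infusion (Protocol Section 9.2).
- Sample size: 40 (Protocol Section 9.2, which allows more).
- Post-infusion window: Day 82 to Day 469 (SAP Section 5.2), so 469 − 82 + 1 = 388 days, and 388/365.25 = 1.062 years.
- Pre-infusion window: at least 0.5 years, no upper limit (SAP Section 6.1.1.1).
- Assumed, because the documents do not give them: dispersion k of 0, 1 or 2; four resumers, each cut off 28 days after Day 82 (0.0767 years) and bleeding at 5.0 per year; all others at 1.5 per year with full follow-up.

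**Formula.** P(no bleed in time t) = exp(−rate × t) for k = 0, otherwise (1 + k × rate × t)^(−1/k).

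**Step 1: size per participant.** 1/40 = 2.5 points. This is the upper limit. It applies to a participant with no counted bleed, relative to counting him as not bleed-free, and it shrinks if more than 40 are dosed.

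**Step 2: effect of short counted time at 5.0 per year.** For k = 1, 28 days gives 1/(1 + 0.383) = 0.723, and 388 days gives 1/(1 + 5.31) = 0.158.

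| k | bleed-free over 28 days | bleed-free over 388 days |
|---|---|---|
| 0 | 68% | 0.5% |
| 1 | 72% | 16% |
| 2 | 75% | 29% |

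**Step 3: reported percentage with 4 resumers in 40.** At 1.5 per year over 1.062 years, P(no bleed) is 0.203, 0.386 or 0.489 for k = 0, 1, 2. For k = 1 the SAP rule gives (36 × 0.386 + 4 × 0.723)/40 = 41.9%. Counting resumers as not bleed-free gives 36 × 0.386/40 = 34.7%.

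| k | SAP rule | resumers not bleed-free | difference (points) |
|---|---|---|---|
| 0 | 25.1% | 18.3% | 6.8 |
| 1 | 41.9% | 34.7% | 7.2 |
| 2 | 51.5% | 44.0% | 7.5 |

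**Step 4: window length alone, same rate of 5.0 per year in both periods.**

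| k | 0.5 years | 1.062 years | 2 years (assumed) |
|---|---|---|---|
| 0 | 8.2% | 0.5% | about 0% |
| 1 | 28.6% | 15.8% | 9.1% |

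With no treatment effect, a pre-infusion period shorter than 388 days makes prophylaxis look better. A longer one makes gene therapy look better.

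**The case against.** The strongest reply is that the exposure is narrow. A reader might infer that treatment failures in general are credited as bleed-free. The documents do not support that: a participant who resumes because of bleeds on or after Day 82 has already bled, and untreated bleeds also count towards the any-bleeding version. Those exposed are mainly resumers on the FIX activity criterion. This stands and limits the point.

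Resumption is also visible elsewhere. SAP Sections 3.2.2 and 6.2.2.2 report the percentage resuming, overall and by interval. AIR counts every infusion, and steady-state FIX:C is imputed as 1.9% after resumption. A careful reader could put these beside the bleed-free percentage, but that does not correct the percentage itself. The Jump to Reference analysis in SAP Section 6.1.1.2 covers ABR for total bleeds only, and the Evaluable set does not help because Section 6.2.6 uses the Dosed population.

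The size is smaller on another yardstick. Had an early resumer instead been followed to Month 15 at 5.0 per year (k = 1), the expected inflation would be (0.723 − 0.158) × 2.5 = 1.4 points each. Choosing between these yardsticks is partly a choice of estimand. SAP Section 2.1.1 also expects loss to follow-up to be rare.

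Finally, a reader might infer that the unequal windows work against the product. That holds only if the pre-infusion period is under 388 days. Half a year is a floor, screening and baseline can be extended, and SAP Section 6.7 notes a pause in dosing, so the direction is unknown.

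**Conclusion.** The point holds within these limits. The SAP applies a rule suited to a rate to a yes/no endpoint, where it can report as bleed-free a participant who resumed with no counted bleed or who was observed for only part of the window. The effect is up to 2.5 points per such participant at n=40. It is about 7 points in the four-resumer illustration, which rests on the assumed number, timing, bleeding rate and dispersion. The pre- and post-infusion percentages are not comparable as defined, and the direction of that bias depends on pre-infusion durations that the documents do not give.

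It would be wrong to infer a threat to the trial's main conclusion. The percentage is summarised descriptively and is absent from the gatekeeping sequence in SAP Section 5.1, so the primary analysis, its power and type I error are untouched. This is a worthwhile clarification with low consequence.

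**What to change.** In SAP Sections 2.1.2.5, 3.2.6 and 6.2.6:
- Count a participant who resumes prophylaxis in or before the window as not bleed-free.
- Handle withdrawals and participants not yet at Month 15 by censoring them in a Kaplan-Meier estimate of time to first bleed from Day 82, with resumption treated as an event. Censoring resumption would not count the failure. Requiring a complete window would wrongly count participants still in follow-up as failures.
- State the denominator for each interval, including for participants who resumed before it began.
- Add one pre/post comparison over equal lengths, for example 6 months from the start of each period, which every participant has before infusion by the entry requirement.

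The cost is SAP wording and one extra table, with no new data. The post-infusion percentage may come out slightly lower.

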2.2. Study Design

This phase 3, open-label, single arm, multi-site study will compare the efficacy following a single intravenous (IV) infusion of PF-06838435 to FIX prophylaxis in the usual care setting, in adult male participants from the lead-in study (C0371004) with severe to moderately severe hemophilia B (FIX:C $\leq 2\%$). Eligible study participants will have completed a minimum 6 months of FIX replacement prophylaxis therapy in the lead-in study (C0371004). The study duration for each participant in this study (C0371002) will be 312 weeks. At least 50 participants who completed study C0371004 will be screened to dose at least 40 participants with PF-06838435, and all participants who are dosed in C0371002 are expected to be evaluable.

Figure 1. Phase 3 Study

* Primary endpoint ABR for total bleeds, as well as key secondary endpoints of AIR, ABR for treated bleeds, and FIX:C will be analyzed from Week 12 to Month 15.

3. ENDPOINTS AND BASELINE VARIABLES: DEFINITIONS AND CONVENTIONS

3.1. Primary Endpoint(s)

ABR_{total} from Week 12 to Month 15 is the primary endpoint of this study.

3.1.1. Annualized Bleeding Rate (ABR) for Total Bleeds

An eDiary, a hand-held device, will be provided to all participants at Visit 1. The participants are required to enter any occurrence of bleeding episodes (including date, time, location, and etiology) and any exogenous FIX replacement (including date, time, reason, and dose) required to treat the bleeds. If bleeding episodes or treatments are not entered in the eDiary during the appropriate time window or due to extenuating circumstances, data should be entered by the investigator (or appropriate site staff member) into a Bleeding case report form (CRF) with appropriate source documentation in the participant's medical record.

When calculating ABR, bleeds will be pooled from both sources (eDiary and Bleeding CRF) to avoid missing reports.

The identification of a new treated bleeding episode is clarified in the Protocol Appendix 7. If a bleed is treated with FIX infusion (according to Bleeding eDiary or Bleeding CRF) within 72 hours post the start of bleeding (by comparing date/time of bleeding to date/time of infusion in Infusion eDiary or Infusion CRF), regardless of the type of treatment (preventive, prophylaxis or rescue medication), it will be considered as a treated bleed. If a bleed is not treated with FIX infusion according to the Bleeding eDiary or the Bleeding CRF, the bleed will not be considered as a treated bleed but considered as an untreated bleed.

For treated bleed, if there are multiple concurrent bleeds (spontaneous or traumatic) on the same date AND time but in different locations in a participant, they will be recorded as one bleed for that participant. However, the bleed will be counted towards all attributable locations in summaries of bleeds of specific site. If concurrent bleeds occurred on the same day but different times and different locations, they will be counted as independent bleeds. On the other hand, if concurrent bleeds occurred on the same day but different times at the SAME location, they will be counted as one bleed.

A bleed is considered a "new untreated bleed" if occurring >72 hours after the previous untreated bleed at the same site or occurring > 72 hours after stopping treatment from the original bleed for which treatment was initiated, or an untreated bleed occurring at a different site from the original bleed regardless of the time (Protocol Appendix 7).

For untreated bleed, every occurrence will be counted as a separate bleed.

The number of bleeding episodes (treated and untreated, excluding procedural bleeds) from Week 12 to Month 15 will contribute to the post-infusion ABR_{total} calculation for each participant, which is the primary endpoint of this study. A noninferiority test of treatment difference in ABR_{total} between pre- and post-infusion with PF-06838435 will be performed, with a NI margin of 3. The endpoint of ABR_{total} will also be calculated for the following designated time periods, such as >Month 15 to Month 24; >Month 24 to Month 36; >Month 36 to Month 48; >Month 48 to Month 60, and >Month 60 to Month 72, and considered as secondary. These secondary endpoints will be referred to as ABR_{total} Year 2, ABR_{total} Year 3, ABR_{total} Year 5, and ABR_{total} Year 6 hereafter in this document.

In addition, ABR_{total} will also be calculated and summarized for the following periods: prior to corticosteroid initiation, during corticosteroid treatment and post-corticosteroid treatment (Section 5.2) for participants in whom corticosteroid are initiated. ABR_{total} during the overall time period (Week 12 to Month 15) for participants who do not have corticosteroid treatment will be presented side by side in the same table.

For participants with incomplete data for the analysis time period, or if a participant has not yet been followed for the full length of the analysis time period, all available data during the analysis period will be annualized and summarized as such. ABR_{total} for each participant will be calculated as below:

 $ABR_{total} = (Number of bleeding episodes (treated and untreated, excluding procedural bleeds) on study during the given$ time period) x 365.25(Date of last day – date of first day +1) in that time period

Bleeding episodes associated with a surgical procedure (perioperative and/or during the surgical rehabilitation period) will not be included in the ABR_{total} calculation.

If prophylaxis FIX regimen is resumed for a participant as defined in Protocol Section 6.5.1, then the time period following the resumption of the prophylaxis regimen will be excluded from the ABR endpoint calculation, which means the bleeding events will be excluded and the time period of observation will be deducted as well. Date and reason of investigator decision to resume FIX prophylaxis will be collected in a CRF. Date of investigator decision will be considered as date of FIX prophylaxis resumption.

The baseline ABR data for total bleeds will be calculated using the above formula and will be based on data collected in the Pre-Infusion Period while participants were on their respective usual care prophylaxis FIX replacement regimen. The baseline ABR will be annualized using the above formula counting bleeds and days in both the lead-in study (C0371004) and the screening period in C0371002 (from date of consent to date of study drug infusion).

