## **10.7. Appendix 7: Bleed and Factor Replacement Regimen Definitions**

### **Definition of a Bleed**

Treated Bleed: An event necessitating administration of coagulation factor within 72 hours of signs or symptoms of bleeding (protocol definition, unless specifically referring to untreated bleed).

Untreated Bleed: A bleeding event not necessitating administration of coagulation factor within 72 hours of signs or symptoms of bleeding.

New Bleed: A bleed occurring >72 hours after stopping treatment from the original bleed for which treatment was initiated or a bleed occurring at a different site from the original bleed regardless of the time from last injection.

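### SAP 3.1.1 counts treated and untreated bleeds by different site-and-time rules, so ABRtotal depends partly on whether FIX was given

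*SAP*

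**What the plan says.** Protocol Appendix 7 (Section 10.7) treats as new a bleed more than 72 hours after treatment of the earlier one has stopped, or "a bleed occurring at a different site from the original bleed regardless of the time from last injection".

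SAP Section 3.1.1 adopts that appendix for treated bleeds: "The identification of a new treated bleeding episode is clarified in the Protocol Appendix 7". It then adds conventions for treated bleeds only:

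- Same date and time, different locations: if they occur "on the same date AND time but in different locations in a participant, they will be recorded as one bleed for that participant". For site tables, however, "the bleed will be counted towards all attributable locations in summaries of bleeds of specific site".
- Same day, different times, different locations: independent bleeds.
- Same day, different times, same location: one bleed.

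For untreated bleeds the same section, again citing Appendix 7, counts as new a same-site bleed more than 72 hours after the previous one, or "an untreated bleed occurring at a different site from the original bleed regardless of the time". The next sentence reads: "For untreated bleed, every occurrence will be counted as a separate bleed".

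A bleed recorded as treated within 72 hours keeps that status whatever the infusion was for: "regardless of the type of treatment (preventive, prophylaxis or rescue medication), it will be considered as a treated bleed". Both types enter the primary endpoint: "The number of bleeding episodes (treated and untreated, excluding procedural bleeds) from Week 12 to Month 15 will contribute to the post-infusion" ABRtotal. The baseline ABR uses the same formula.

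**The concern.** ABRtotal is meant to measure bleeding. Under these rules it also measures FIX use. A fall that starts a knee bleed and an elbow bleed at 10:00 scores 2 if left untreated and 1 if treated. If the participant enters 10:00 and 10:05 and treats both, it scores 2 again. Two entries on one day for one joint score 1 if treated; if untreated, the closing sentence makes them 2 and the 72-hour rule makes them 1.

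The comparison is pre/post within participants, with no concurrent control. Baseline is collected on prophylaxis, and prophylaxis is suspended after infusion. Because an infusion of any type can make a recorded bleed a treated one, the treated share may differ between the periods, and the merging rules would then apply at different rates on the two sides of the contrast. A change in treatment habit alone could move the difference.

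The same counts feed ABRtreat, the superiority tests of ABRtreat and ABRtotal, and the tests by bleed type, which include untreated bleeds (SAP Table 2). None of the four sensitivity analyses in SAP Section 6.1.1.2 varies the counting rule, so its effect would not be seen.

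**Working it through.** **Inputs from the documents.** Planned ABRtotal of 5.0 before and 1.5 after infusion, margin 3.0 bleeds/year, 40 participants, one-sided alpha 0.025, power at least 90% (Protocol Section 9.2). Pre-infusion duration at least 0.5 year (SAP Section 6.1.1.1). Post-infusion window Day 82 to Day 469 (SAP Section 5.2), so 469 − 82 + 1 = 388 days, or 1.062 years.

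**Assumptions.** The documents do not give m, the share of bleeding events that hit two sites at one time stamp (range used: 5% to 20%), or a, the share of events treated in each period. Nor do they give the negative binomial dispersion k or the within-participant correlation.

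**The plan's power figure.** A Wald approximation with zero correlation gives SE² = [5/0.5 + 25k + 1.5/1.062 + 2.25k]/40 and power = Φ((3 + 3.5)/SE − 1.96). At k = 2, SE = 1.284 and power is 99.9%. Power stays at or above 90% up to k of about 5.5. The figure cannot be reproduced exactly without k, and this point does not dispute it.

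**One participant, one two-site event.** In the 388-day window: 365.25/388 = 0.94 per year if treated, 2 × 0.94 = 1.88 if not. In a 183-day baseline (an assumed length near the six-month minimum): 2.00 or 3.99.

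**Group level.** With event rate λ:

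- SAP rule: λ[1 + m(1 − a)]
- one bleed per site for both types: λ(1 + m)
- merged for both types: λ

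*Equal true rate of 5.0 in both periods.* The SAP rule creates a false post-minus-pre difference of 5.0 × m × (a_pre − a_post):

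| m | 80% treated before, 50% after | 70% before, 30% after |
|---|---|---|
| 5% | +0.075 | +0.10 |
| 10% | +0.15 (5.25 − 5.10) | +0.20 |
| 20% | +0.30 | +0.40 (5.70 − 5.30) |

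Swapping the treated shares reverses the sign.

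*Planned event rates of 5.0 and 1.5, with 90% treated before and 50% after:*

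| m | SAP rule | One per site | Merged |
|---|---|---|---|
| 10% | 1.575 − 5.05 = −3.475 | 1.65 − 5.50 = −3.85 | −3.50 |
| 20% | 1.65 − 5.10 = −3.45 | 1.80 − 6.00 = −4.20 | −3.50 |

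Most of the gap between the SAP rule and one bleed per site is a change of unit, since both rates are multiplied by 1 + m. Against merging throughout, the SAP rule differs by only 0.025 and 0.05.

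*Extremes at m = 20%.* All treated before and none after: SAP rule 1.8 − 5.0 = −3.20. None before and all after: 1.5 − 6.0 = −4.50. Moving from the SAP rule to one per site shifts the difference by −1.00 and +0.30 respectively; moving to merging shifts it by −0.30 and +1.00. Across these scenarios, power at k = 2 stays above 99% under the SAP rule and under one bleed per site.

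**ABRtreat.** Against one bleed per site it is lower by m/(1 + m): 4.8%, 9.1% and 16.7% at m = 5%, 10% and 20%. If m is the same in both periods, the post/pre ratio is unchanged.

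**Same-site part.** The documents give nothing to size it. The SAP formula applies in the same form if m is read as the share of events with a second entry that is counted only when untreated.

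**The case against.** A reader might infer that the SAP breaches the protocol's bleed definition. The documents do not support that. Appendix 7 defines a new bleed relative to an earlier one and to the time since the last injection, and does not expressly cover two bleeds that start together. Where the sequence is clear, the SAP follows it: different sites at different times are independent. The protocol also lets the SAP describe minor changes in statistical methodology. What stands against the SAP is narrower: it cites the same appendix for both bleed types and reads it in opposite ways.

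Counting one fall as one episode is a defensible convention, and site information is kept for the location tables. That stands, but such a convention would have to cover untreated bleeds too.

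The sentence on untreated occurrences could be read as referring only to bleeds already classed as new. That reading removes the conflict with the 72-hour rule, but the text does not say so, and the different-site asymmetry remains.

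Bias needs both a material m and a shift in treated share, and neither is in the documents. That is correct, so the sizes above are illustrations and not estimates.

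**Conclusion.** The counting rules for treated and untreated bleeds are inconsistent, and ABRtotal depends partly on whether FIX was given. Under the assumed inputs the false difference is a few tenths of a bleed per year or less in plausible cases, of either sign. If fewer bleeds are treated once prophylaxis stops, it works against the product; if more are treated, it works in its favour.

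It would be tempting to conclude that the primary result is at risk or tilted towards the product. The documents support neither. At rates near the planned 5.0 and 1.5, every scenario leaves the difference at −3.20 or below, against a margin of +3.0. Even with equal true rates, +0.15 to +0.40 is 5% to 13% of the margin. The issue matters more for the superiority tests, where the margin is 0, and for the reported ABRs. It should be corrected but does not undermine the primary test.

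**What to change.** In SAP Section 3.1.1, before database lock, apply one site-and-time rule to treated and untreated bleeds alike, in the Pre-Infusion Period and in all post-infusion windows:

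- By default, use the Appendix 7 different-site rule and the same more-than-72-hour rule for bleeds at one site, in place of the treated-only conventions.
- Remove the sentence on counting every untreated occurrence, or reconcile it with the 72-hour rule.
- Report ABRtotal and ABRtreat with simultaneous multi-site bleeds merged for both types as a sensitivity analysis.
- State in Appendix 7 or the SAP how bleeds with the same time stamp are handled.

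Deleting only the same-time merging rule would not be enough, because the same-location rules would still differ by FIX use.

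The cost is SAP wording and derivation code. Reported ABRs change slightly in both periods. This study's eDiary collects bleed date, time and location, but most baseline data come from lead-in study C0371004, whose diary fields are not described in these documents. It must be confirmed that C0371004 recorded bleed location and time.
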